9.4.7 Exploratory Analyses

The exploratory outcome measures for this study include but are not limited to the following:

- Molecular Response by percent reduction in baseline JAK2V617F (or JAK2 exon 12 mutation) allele burden at end of Cycle 3, end of Cycle 5, Week 32, and every 3 cycles up to 2 years post initial dose compared to baseline. Other genes potentially relevant to PV and/or to drug response may also be assessed at different timepoints.
- Histologic Response changes in bone marrow histopathologic abnormalities and reduction in baseline reticulin/collagen fibrosis (with fibrosis grading per European consensus on grading bone marrow fibrosis and assessment of cellularity (Thiele et al. 2005) at Week 32, and every 6 cycles per Principal Investigator (PI)'s discretion in context of CHR up to 2 years post initial dose compared to baseline.
- Assessment of Cytogenetic Response at Week 32, and every 6 cycles per PI discretion in context of CHR up to 2 years post initial dose compared to baseline.

9.5 INTERIM ANALYSES

No formal testing for efficacy will be carried out in this study and therefore no prospectively planned interim analyses are planned. The Sponsor may review the data at various timepoints during the course of the study to evaluate information that may emerge during the course of this study.

Interim analyses may be performed and interpreted by members of the Sponsor study team and senior management personnel as appropriate.

9.6 SUMMARIES OF CONDUCT OF STUDY

Enrollment, major protocol violations, and discontinuations from the study will be listed. The incidence of treatment discontinuation for reasons other than disease progression will be tabulated.

Variables from the eCRF used to establish the number of patients who reached the various stages of the study, withdrew, and the reasons for withdrawal will be described in the SAP.

11. APPENDICES

The following section includes standard appendices including:

- Regulatory, Ethical, and Study Oversight Considerations ([Appendix 7](#)).
- Adverse Events: Definitions and Evaluating, Followup and Reporting ([Appendix 10](#)).
- Procedures for Recording Adverse Events ([Appendix 11](#)).
- Contraceptive Guidance and Collection of Pregnancy Information ([Appendix 6](#)).

Additional study-related appendices are in order of appearance in the protocol.

Appendix 1

Modified ELN Criteria for Hematologic Response in PV Patients

Response Grade	Definition
Complete response (CR)	(1) Hct < 45% without phlebotomy * AND (2) Platelet count $\leq 400 \times 10^9/L$ AND (3) White blood cell count $\leq 10 \times 10^9/L$, AND (4) Normal spleen size on imaging AND (5) No disease-related symptoms#
Partial response (PR)	In patients who do not fulfill the criteria for complete response: Hct < 45% without phlebotomy * OR response in 3 or more of the other criteria.
No response (NR)	Any response that does not satisfy partial response.
Progressive disease (PD)	Defined by occurrence of increased bone marrow fibrosis from baseline, and/or transformation to MF, MDS or Acute Leukemia.

* Defined as protocol-specified ineligibility for phlebotomy between Weeks 8–32 and ≤ 1 instance of phlebotomy eligibility between first dose and Week 8. (Definition of eligibility for phlebotomy: a Hct of $\geq 45\%$ that was $\geq 3\%$ higher than baseline level or a Hct of $> 48\%$.)

Disease-related symptoms as described in Section 8.3.8.

Reference

Adapted from: Barosi G, Birgegard G, Finazzi G, et al. Response criteria for essential thrombocythemia and polycythemia vera: result of a European LeukemiaNet consensus conference. *Blood*. 2009;113:4829–33.

Appendix 2

Molecular Response Criteria for PV Patients

Response Grade	Definition
Complete response	Reduction of any specific molecular abnormality to undetectable levels.
Partial response*	(1) A reduction of $\geq 50\%$ from baseline value in patients with $< 50\%$ mutant allele burden at baseline OR (2) A reduction of $\geq 25\%$ from baseline value in patients with $> 50\%$ mutant allele burden at baseline.
No response	Any response that does not satisfy partial response.

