 - Platelet (PLT) count $> 400 \times 10^9/L$ and white blood cell (WBC) count $> 10 \times 10^9/L$ after 3 months of HU.
 - Failure to reduce splenomegaly extending > 10 cm below the costal margin by $> 50\%$, as measured by palpation after 3 months of HU.
 - Intolerance to HU is defined as at least one of the following:
 - Absolute neutrophil count (ANC) $< 1.0 \times 10^9/L$.
 - PLT count $< 100 \times 10^9/L$ or hemoglobin < 100 g/L (i.e., 10 g/dL) at the lowest dose of HU required to achieve a response.
 - Presence of leg ulcers or other unacceptable HU-related non-hematologic toxicities (such as mucocutaneous manifestations, GI symptoms, pneumonitis, or fever at any dose of HU).

For patients previously exposed to ruxolitinib, inclusion requires the following in addition to previous treatment for myeloproliferative disorder with HU:

- *Therapy resistant PV after at least 6 months of treatment with ruxolitinib, defined by at least one of following:*
 - *Need for phlebotomy to achieve Hct $< 45\%$, at least two over 6 months*
 - *Uncontrolled leukocytosis (WBC count $> 10 \times 10^9/L$)*
 - *Uncontrolled thrombocytosis (PLT count $> 400 \times 10^9/L$)*
 - *Failure to achieve a $> 50\%$ reduction in palpable splenomegaly measuring > 5 cm from the left costal margin or failure to become non-palpable in palpable splenomegaly measuring 0–5 cm*
 - *Inadequately controlled disease-related symptoms (e.g., pruritus, headache, night sweats, excluding fatigue) after excluding other causes*
- *Ruxolitinib intolerance defined as at least one of following at lowest dose of ruxolitinib to achieve adequate response:*
 - *Cytopenia defined as one or more of the following:*
 - Neutropenia, ANC $< 1.0 \times 10^9/L$*
 - Thrombocytopenia, PLT count $< 100 \times 10^9/L$*
 - Anemia, hemoglobin < 10 g/dL*
 - *Life threatening infections deemed associated with ruxolitinib or other infections complications possibly associated with ruxolitinib (shingles, TB, hepatitis reactivation) at any time during study treatment*

- *Non-melanoma skin cancer (recurrence of or multiple) at any time during study treatment*
- 7. *Adverse events likely caused by ruxolitinib (assessment of attending physician) and that is of a severity that precludes further treatment with ruxolitinib (as per judgment of the attending physician and the patient)*
- 8. Eastern Cooperative Oncology Group (ECOG) performance status of 0 to 1.

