8.2.6 Medical History and Demographic Data

Medical history includes clinically significant diseases, surgeries, PV history (including prior PV therapies, HU therapy, and phlebotomies), reproductive status and all medications (e.g., prescription drugs, over-the-counter drugs, herbal or homeopathic remedies, nutritional supplements) used by the patient within 28 days prior to the screening visit.

PV has specific constitutional symptoms associated with the disease such as fever, night sweats, pruritus, microvascular disturbances, headaches, abdominal swelling and weight loss. Any specific PV symptoms should be clearly documented if present at baseline in the patients PV Medical History eCRF. Ongoing treatments specific to these conditions should be noted on the Targeted previous and concomitant medicines eCRF.

Demographic data will include age, sex, and self-reported race/ethnicity.

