8.3.8 Disease-Related Events and/or Disease-Related Outcomes Not Qualifying as AEs or SAEs

The following disease-related events (DREs) are common in patients with PV and can be serious/life-threatening:

- Fever, in the absence of neutropenia
- Abdominal swelling without known organomegaly
- Pruritus
- Fatigue
- Early satiety

- Night sweats
- Splenomegaly

If present at baseline and related to PV, the event should be added to the PV Medical History eCRF and marked as ongoing with or without treatment, indicating any ongoing treatments on the Previous and Concomitant Treatments (Targeted - Polycythemia Vera Associated) eCRF.

Because these events are typically associated with the disease under study, they will not be reported as AEs or according to the standard process for expedited reporting of SAEs even though the event may meet the definition of a SAE.

NOTE: However, if either of the following conditions applies, then the event must be recorded and reported as an SAE (instead of a DRE):

- The event is, in the Investigator's opinion, of greater intensity, frequency, or duration than expected for the individual patient.

OR

- The Investigator considers that there is a reasonable possibility that the event was related to treatment with the investigational product.

Events considered related to PV will instead be recorded on the PV Medical History eCRF with any treatments administered noted on the Previous and Concomitant Treatments (Targeted - Polycythemia Vera Associated) eCRF. In the event that a patient achieves a CHR at Week 32, then subsequent episodes of these events should be reported as AEs.

These DREs will be reviewed by the Medical Monitor.

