8.3.9 Management of Specific Adverse Events

The safety profile of idasanutlin is currently available at higher dose regimens than those to be investigated in this study *and primarily based on patients with solid tumor or AML*. At such higher doses the following identified risks are present: diarrhea; nausea; vomiting; decreased appetite/anorexia; fatigue/asthenia; thrombocytopenia and increased hemorrhagic risk; neutropenia and febrile neutropenia; anemia; pyrexia; sepsis; pneumonia; fungal infections; electrolyte disorders; tumor lysis syndrome. Thrombocytopenia and GI toxicity are dose/exposure dependent but are not expected to occur as severe events at the dose levels investigated in this study. In case of occurrence of events different from those outlined below, guidelines to manage the risk can be found in the [Idasanutlin IB](#).

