5.7.2.1 ELN Hematologic response criteria

Similarly to be evaluated on the 3 Rux naïve populations: without splenomegaly, with splenomegaly; and with and without splenomegaly

Response grade	Definition
Complete response (CR)	(1) Hct < 45% without phlebotomy AND (2) Platelet count $\leq 400 \times 10^9/L$ AND (3) White blood cell count $\leq 10 \times 10^9/L$, AND (4) Normal spleen size on imaging AND (5) No disease-related symptoms*
Partial response (PR)	In patients who do not fulfill the criteria for complete response: Hct < 45% without phlebotomy OR response in 3 or more of the other criteria.
No response (NR)	Any response that does not satisfy partial response.
Progressive disease (PD)	Defined by occurrence of increased bone marrow fibrosis from baseline, and/or transformation to MF, MDS or Acute Leukemia.

* Disease-related symptoms as described in Section

t_ef_rsp

- Response Rate Summary

Patients were classified as “Not Evaluable” if all post-baseline response assessments were reported as not evaluable, or SD assessment occurring within xxx weeks from baseline/study entry.

Patients were classified as “Missing” if no post-baseline response assessments were available.

Note: Time points as per the protocol assessment schedule.

Responder: Is defined as either CR / PR.

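### The ELN symptom criterion borrows a list that contains splenomegaly, already scored as criterion 4, and omits headache and microvascular symptoms, so some ELN grades can come out wrong

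*Protocol*

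**What the plan says.** Appendix 1 of the protocol grades ELN response on five criteria: hematocrit without phlebotomy, platelets, white cells, spleen ("4) Normal spleen size on imaging AND") and symptoms ("5) No disease-related symptoms"). Complete response (CR) needs all five. Partial response (PR) needs either the hematocrit criterion alone or at least three of the other four. Anything less is no response (NR).

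The symptom criterion carries the footnote "Disease-related symptoms as described in Section 8.3.8". Section 8.3.8 lists seven items: fever without neutropenia, abdominal swelling without known organomegaly, pruritus, fatigue, early satiety, night sweats and splenomegaly. The main purpose of that section is AE reporting: "Because these events are typically associated with the disease under study, they will not be reported as AEs".

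Two other protocol sections describe PV symptoms differently:
- The ruxolitinib-resistance entry criterion in Section 5.1 reads "Inadequately controlled disease-related symptoms (e.g., pruritus, headache, night sweats, excluding fatigue) after excluding other causes".
- Section 8.2.6 says "PV has specific constitutional symptoms associated with the disease such as fever, night sweats, pruritus, microvascular disturbances, headaches, abdominal swelling and weight loss".

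SAP 5.7.2.1 repeats the ELN table. Its footnote reads "Disease-related symptoms as described in Section", with no section number after it in the text available. The SAP gives no symptom list of its own and counts CR or PR as a responder.

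**The concern.** A list written mainly to decide what is reported as an adverse event is being used to score an efficacy criterion, and it fits badly in two places.

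First, it contains an organ finding that the same table already scores separately. One abnormality then counts against the patient twice, under a PR rule that works by counting criteria.

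Second, it leaves out symptoms that the protocol names elsewhere. The clearest case is headache, which can qualify a patient for the ruxolitinib-resistant cohort but has no bearing on whether that patient is later called symptom-free.

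ELN response and its duration are secondary endpoints in both cohorts. The ELN grade also appears in the treatment-continuation text of Sections 6.6 and 7.1. A grade that depends on the borrowed list therefore reaches a little beyond one table.

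**Working it through.** The plan states no figure for ELN response, and the sample-size probabilities in Protocol 9.2 use only composite response, Hct control and CHR. There is nothing to reproduce, so the check applies the Appendix 1 rules directly.

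**Rules.** Let H, P, W, S and Y be 1 if the hematocrit, platelet, white-cell, spleen and symptom criteria are met, and 0 otherwise.
- CR: H = P = W = S = Y = 1.
- PR: not CR, and either H = 1 or P + W + S + Y ≥ 3.
- NR: otherwise.

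**Splenomegaly counted twice.** Under 8.3.8 as written, S = 0 forces Y = 0.
- With an enlarged spleen, P + W + S + Y ≤ 1 + 1 + 0 + 0 = 2. This is below 3, so the counting route to PR is closed.
- Take H = 0, P = W = 1, S = 0 and no other symptom. As written the sum is 1 + 1 + 0 + 0 = 2, so NR. With splenomegaly left to criterion 4 it is 1 + 1 + 0 + 1 = 3, so PR.
- CR cannot change, because S = 0 already rules it out.
- If H = 1 the patient is PR either way.

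**Headache and microvascular symptoms omitted.** Take a patient whose only remaining symptom is one of these.
- With H = P = W = S = 1: as written Y = 1, so CR. If the symptom counts, Y = 0, so PR. The patient is a responder both ways.
- With H = 0, S = 1 and exactly one of P and W met: as written the sum is 1 + 1 + 1 = 3, so PR. If the symptom counts it is 1 + 1 + 0 = 2, so NR.

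**All combinations.** There are seven yes/no states: the four non-symptom criteria, other 8.3.8 symptoms, headache or microvascular symptoms, and fatigue. They give 2^7 = 128 combinations. Each was graded as written, then under three changes.

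| Change to criterion 5 | Grades that move | Where |
|---|---|---|
| Remove splenomegaly only | 2 NR to PR | No Hct control |
| Add headache/microvascular only | 1 CR to PR; 2 PR to NR | CR to PR with Hct control; PR to NR without |
| Both | 1 NR to PR; 1 CR to PR; 2 PR to NR | CR to PR with Hct control; the rest without |

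With both changes 4 of 128 combinations move. These are counts of logical states, not patient frequencies. In no row does CR-or-PR status change when hematocrit is controlled.

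**Illustrative size.** Symptom prevalence is not in the documents. Assume 10 of 20 patients otherwise meet CR, and that 5% to 30% of those have only headache or microvascular symptoms. Then 10 × 0.05 = 0.5 to 10 × 0.30 = 3 patients move from CR to PR. That is 0.5/20 = 2.5 to 3/20 = 15 percentage points of the CR rate. Both inputs are assumptions.

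**The case against.** The best defence is that Appendix 1 is openly a modified set of criteria and defines its symptom item explicitly. Section 6.5.1 also uses 8.3.8 as the definition of PV-related symptoms, so the footnote is not a stray reference. The lists it is compared with are open: 5.1 gives examples and 8.2.6 says such as. All of this stands. A reader might infer that ELN responses as a whole are misclassified. The documents do not support that, because they fix no single reference list. What they support is that particular grades can be wrong or inconsistent.

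A reader might also infer that fatigue does not belong in the criterion, since 5.1 excludes it and Section 8.3.9 lists it among idasanutlin risks ("diarrhea; nausea; vomiting; decreased appetite/anorexia; fatigue/asthenia"). That does not hold. Sections 4.2.1, 4.2.3 and 8.3.9.3 and the MPN-SAF TSS all treat fatigue as a feature of PV. The 8.3.9 risk list refers to doses higher than those in this study. Section 8.3.8 also takes an event out of the disease-related category once the investigator sees a reasonable possibility of relation to treatment, so fatigue judged drug-related does not count under the list. The exclusion in 5.1 is an eligibility choice.

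Nor would replacing 8.3.8 by 8.2.6 be a clean repair, because 8.2.6 omits early satiety.

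Splenomegaly could be argued to be a sign that nobody would score as a symptom. The footnote makes no such exception, however, so a literal derivation would count it. The incomplete SAP footnote may be a loss in text conversion, and no weight is placed on it.

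**Conclusion.** The point holds in limited form. Listing splenomegaly under the symptom criterion is redundant with criterion 4. Read literally, it grades NR instead of PR in one situation: no hematocrit control, normal platelets and white cells, enlarged spleen, no other listed symptom. It never alters CR. The omission of headache and microvascular symptoms is an inconsistency with 5.1 and 8.2.6. It lets a patient enrolled for headache be graded CR with that headache unchanged, and it can also turn NR into PR in patients without Hct control.

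The consequences stay within a descriptive secondary endpoint, its duration, and text that uses the ELN grade. The definitions of Hct control, composite response and CHR contain no symptom item. The number of patients affected is unknown, and the 2.5 to 15 point range rests wholly on assumed prevalences. The point is worth correcting because the splenomegaly repair costs almost nothing. It does not threaten the primary results.

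**What to change.** In the Appendix 1 footnote and in SAP 5.7.2.1:
- State that splenomegaly is excluded from criterion 5 because it is scored under criterion 4.
- Keep the other 8.3.8 symptoms, including fatigue and early satiety.
- Add headache and microvascular symptoms where recorded, and reconcile the wording with 5.1 and 8.2.6.
- Write the section reference and the symptom list out in full in the SAP, with the data source and time point used to decide that no symptoms are present.
- Show ELN CR without fatigue as a sensitivity row only.

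The cost is two footnotes, one derivation and re-derivation of grades already assigned. One limitation should be stated alongside. Section 8.2.6 requires PV symptoms to be documented when present at baseline, and headache is not an MPN-SAF TSS item. On-study headache may therefore be recorded only through the AE or PV Medical History eCRF, and its status at Week 32 may be incomplete.

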Appendix 3 Fibrosis Grading and Histologic Response Criteria for PV Patients

Fibrosis Grading per European Consensus 2005:

Grade	
0	Scattered linear reticulin with no intersections (cross-overs) corresponding to normal bone marrow.
1	Loose network of reticulin with many intersections, especially in perivascular areas.
2	Diffuse and dense increase in reticulin with extensive intersections, occasionally with only focal bundles of collagen and/or focal osteosclerosis.
3	Diffuse and dense increase in reticulin with extensive intersections with coarse bundles of collagen, often associated with significant osteosclerosis.

Histologic Response Criteria:

Response
Histologic Remission (including disappearance of trilineage hyperplasia, age-adjusted normocellularity and absence of reticulin fibrosis [Grade 0])
No change from Baseline
Worsening of Histology from Baseline*

* If “Worsening of Histology from Baseline” is recorded please review and select the “Details of Transformation” from the following list.

- Transformation to Myelofibrosis
- Transformation to MDS
- Transformation to Acute Leukemia
- No Transformation

References

Appendix 4

WHO 2016 Diagnostic Criteria For PV

2016 WHO diagnostic criteria for PV

(Diagnosis of PV requires meeting either all 3 major criteria, or the first 2 major criteria and the minor criterion)

Major criteria

Criterion 1 (clinical)	
Hb, or	>16.5 g/dL in men, > 16.0 g/dL in women
Hematocrit, or	>49% in men, >48% in women
Red cell mass	Increased 25% above mean normal predicted value
Criterion 2 (morphologic)	
BM morphology*	Hypercellularity for age with trilineage growth (panmyelosis), including prominent erythroid, granulocytic, and megakaryocytic proliferation with pleomorphic, mature MKs (differences in size)
Criterion 3 (genetic)	
JAK2V617F, or	Presence
JAK2 exon 12 mutation	Presence
Minor criterion	
Serum Epo level	Subnormal

*Criterion number 2 (BM biopsy) may not be required in cases with sustained absolute erythrocytosis: hemoglobin levels > 18.5 g/dL in men (hematocrit, 55.5%) or > 16.5 g/dL in women (hematocrit, 49.5%) if major criterion 3 and the minor criterion are present.

Reference

Appendix 5

Cockcroft Gault Formula for Calculation of Creatinine Clearance

Creatinine Clearance (mL/min) for Males:

$$\text{Creatinine Clearance} = \frac{(140 - \text{age [years]} \times \text{body weight [kg]})}{(72 \times \text{serum creatinine [mg/dL]})}$$

Creatinine Clearance (mL/min) for Females:

$$\text{Creatinine Clearance} = \frac{(140 - \text{age [years]} \times \text{body weight [kg]})}{(72 \times \text{serum creatinine [mg/dL]})} \times 0.85$$

Appendix 6

Contraceptive Guidance and Collection of Pregnancy Information

1. DEFINITIONS

Woman of Childbearing Potential (WOCBP)

A woman is considered fertile following menarche and until becoming post-menopausal unless permanently sterile.

Women in the following categories are not considered WOCBP

- a) Pre-menarchal
- b) Pre-menopausal female with one of the following:
 - Documented hysterectomy.
 - Documented bilateral salpingectomy.
 - Documented bilateral oophorectomy.

Note: Documentation can come from the site personnel's: review of participant's medical records, medical examination, or medical history interview.

- c) Post-menopausal female
 - A post-menopausal state is defined as no menses for 12 months without an alternative medical cause other than menopause. A high follicle-stimulating hormone (FSH) level in the post-menopausal range may be used to confirm a post-menopausal state in women not using hormonal contraception or hormonal replacement therapy (HRT). However, in the absence of 12 months of amenorrhea, a single FSH measurement is insufficient.
 - Females on HRT and whose menopausal status is in doubt will be required to use one of the non-hormonal highly effective contraception methods if they wish to continue their HRT during the study. Otherwise, they must discontinue HRT to allow confirmation of post-menopausal status before study enrollment.

